5.7 PRIOR AND CONCOMITANT MEDICATIONS

Prior medicines are defined as any medicines taken before the date of first dose of study drug.

Concomitant medicines are defined as any medicines taken on or after the date of first dose of study drug. Any medicines taken after the date of last dose of study drug will not be considered concomitant medicines. Both prior and concomitant medicine use will be summarized by the number and percentage of patients in each treatment group receiving each medicine within each

therapeutic class for the ITT Population. Multiple medicines used by a patient in the same category (based on Anatomical-Therapeutic-Chemical classification) will only be counted once.

5.8 MAJOR PROTOCOL DEVIATIONS

Major protocol deviations will be identified and documented based on a review of protocol deviations before database lock and treatment unblinding, and will be used to define the PP population. The categories of major protocol deviations to be reviewed include, but are not limited to, patients who:

- Did not meet key inclusion/exclusion criteria
- Received disallowed concomitant medication that could meaningfully impact results
- Had overall treatment compliance rate <80% or >120%

The number and percentage of subjects with major protocol deviations will be summarized by type of deviation and by treatment group for the ITT Population. All major protocol deviations will be presented in a data listing.

5.9 EFFICACY ANALYSES

All efficacy analyses will be based on the ITT and PP Populations.

Corresponding with the primary efficacy objective of the trial, the primary inference for hypothesis testing is the treatment difference between the placebo group and the IW-1973 groups on the change from baseline in log UACR over Weeks 8 and 12. The primary efficacy analysis will be conducted using the ITT population using a mixed-effects model repeated measures (MMRM) analysis with change from baseline in log-transformed UACR as the response variable, treatment, site, visit, treatment-by-visit interaction, and baseline eGFR stratum as fixed effects, and baseline log UACR and baseline MAP as covariates with unstructured as the variance-covariance structure. Treatment differences between the pooled IW-1973 dose groups and the placebo group will be estimated overall. The null hypothesis of the test will be interpreted as equality between the placebo and pooled treatment groups, and rejection of the null hypothesis as evidence that the pooled IW-1973 groups have a greater effect on lowering UACR than the placebo group. If the null hypothesis is rejected, the nature of these differences

will be explored further by estimating the treatment differences between each IW-1973 dose group and the placebo group overall and at each assessment timepoint. Least square (LS) means, and LS mean differences between each IW-1973 group and placebo, and their associated one-sided 95% confidence intervals will be calculated overall and for each assessment timepoint. The contrasts between each IW-1973 dose group and the placebo group at each assessment timepoint will be compared using a one-sided significance level of 0.05. If the treatment-by-visit interaction is significant at the 0.1 significance level, LS mean treatment differences relative to the previous visit will also be presented.

All change-from-baseline efficacy parameters will use the same MMRM model.

Treatment group differences in the proportion of patients who achieved a 30% or 40% reduction in UACR from baseline to Week 12 will be analyzed using Cochran-Mantel-Haenszel (CMH) test stratified by baseline eGFR stratum.

Summary statistics will be presented by treatment group for the biomarker parameters. Change from baseline in these variables will also be presented, where applicable.

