3.8.8.3 Urine Albumin Creatinine Ratio (UACR)

UACR will be calculated as urine albumin (mg/dL) / urine creatinine (g/dL).

Urine albumin and urine creatinine levels will be determined as part of the clinical laboratory tests ([Table 4](#)). At the Screening Visit, a single urine sample, which may not be first void, will be collected for determination of albumin and creatinine levels. For subsequent study visits, patients will be given urine collection supplies and will collect 2 first-void urine samples on the 2 consecutive mornings before each scheduled visit.

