4.1.2 Primary Efficacy

- Change from baseline in UACR over Weeks 8 and 12

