5.2 DETERMINATION OF SAMPLE SIZE

Using an estimate of standard deviation of 0.67, (29) a sample size of 40 patients per treatment group would provide approximately 80% power to detect a mean between-group difference of -0.376 units in change from baseline in log-transformed UACR over 12 weeks, with a one-sided significance level of 0.05 for at least 1 dose versus placebo comparison. This difference corresponds to a 31% between-group reduction of geometric mean change from baseline in UACR. Assuming a drop-out rate of 20%, approximately 150 patients will be randomly assigned in a 1:1:1 ratio (approximately 50 patients per treatment group) to 20 mg IW-1973, 40 mg IW-1973, or placebo.

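### Does estimating the pooled contrast 'overall' separate the primary test from the declared Weeks 8 and 12 endpoint?

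*Protocol*

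**What the plan says.** Section 4.1.2 gives the primary efficacy endpoint as "Change from baseline in UACR over Weeks 8 and 12". Section 5.9 opens by stating that the primary inference compares placebo with "the IW-1973 groups on the change from baseline in log UACR over Weeks 8 and 12". The synopsis uses the same window in both places.

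Section 5.9 then describes a mixed model for repeated measures (MMRM) with visit and treatment-by-visit terms, and continues: "Treatment differences between the pooled IW-1973 dose groups and the placebo group will be estimated overall". The synopsis repeats that sentence. If the pooled null hypothesis is rejected, each dose is compared with "the placebo group overall and at each assessment timepoint". A further display is conditional: "If the treatment-by-visit interaction is significant at the 0.1 significance level, LS mean treatment differences relative to the previous visit will also be presented".

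Section 3.8.8.3 says that, after Screening, patients "will collect 2 first-void urine samples on the 2 consecutive mornings before each scheduled visit". After baseline this means Weeks 1, 4 and 8, End of Treatment (Day 87) and Follow-up (Day 115). Section 5.2 expresses the planning difference as "units in change from baseline in log-transformed UACR over 12 weeks".

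Section 5.1 leaves further statistical detail to the SAP, to be final before the study is unblinded. The SAP was not available for this review.

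**The concern.** The sentence that introduces the tested contrast does not repeat the Weeks 8 and 12 window. In an MMRM with treatment-by-visit terms, an overall treatment difference is often the equal-weight average across every visit in the model. Three features of the text seem to point that way:

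- *Overall* is paired with individual timepoints.
- Comparisons with the preceding visit are planned.
- UACR is collected at every visit.

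Section 5.2 adds a third time phrase.

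If the all-visit reading were used, the primary test would include Weeks 1 and 4, and perhaps the off-drug Follow-up. It would then answer a different question from the declared endpoint. It would also dilute the effect if the UACR response takes weeks to develop. Because the pooled test precedes the dose-level comparisons, the ambiguity would carry into those as well.

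**Working it through.** **1. The plan's own figure.** Inputs from section 5.2: SD 0.67, difference 0.376 on the log scale, 40 per group, one-sided 0.05.

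- SE = 0.67 × √(2/40) = 0.1498
- Power = Φ(0.376/0.1498 − 1.645) = Φ(0.865) = 0.806, or 0.800 with the noncentral t on 78 df
- 1 − exp(−0.376) = 31.3%; 40/0.8 = 50 per group, 150 in total

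The stated 80%, 31% and 150 all reproduce. The sizing arithmetic is not in question.

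**2. What the two readings would cost.** The protocol gives neither a between-visit correlation nor a time course, so these are assumptions: SD 0.67 at each visit, equal correlation r, 80 pooled against 40 placebo evaluable patients, and the full 0.376 at Weeks 8 and 12.

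For a mean of k visits, SE = 0.67 × √[(1 + (k − 1)r)/k] × √(1/80 + 1/40), and power = Φ(effect/SE − 1.645).

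At r = 0.7, SE is 0.1196 for Weeks 8 and 12 and 0.1142 for Weeks 1, 4, 8 and 12. In the table, the onset column gives the share of the later effect present at Week 1 / Week 4. A 50%/90% onset, for example, gives 0.376 × (0.5 + 0.9 + 1 + 1)/4 = 0.320.

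| Contrast and onset | Mean effect | Reduction | Power r = 0.5 | r = 0.7 | r = 0.85 |
|---|---|---|---|---|---|
| Weeks 8 and 12 | 0.376 | 31% | 0.956 | 0.933 | 0.914 |
| Four visits, 100%/100% | 0.376 | 31% | 0.978 | 0.950 | 0.924 |
| Four visits, 50%/90% | 0.320 | 27% | 0.929 | 0.876 | 0.834 |
| Four visits, 25%/75% | 0.282 | 25% | 0.865 | 0.795 | 0.746 |
| Four visits, 0%/50% | 0.235 | 21% | 0.741 | 0.660 | 0.609 |

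The four-visit average loses power when the mean share at Weeks 1 and 4 falls below 2 × SE₄/SE₂ − 1. That is 0.83, 0.91 and 0.96 at r = 0.5, 0.7 and 0.85.

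If SD 0.67 is instead taken to describe the Weeks 8 and 12 average, SE = 0.67 × √(1/80 + 1/40) = 0.1297 and power for that contrast is 89.5%.

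So the two readings can differ materially. The question is whether the text actually supports the second.

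**3. The wording, side by side.**

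- *The governing sentence.* The first sentence of the section 5.9 paragraph names the primary hypothesis-testing inference and its window. The sentence with *overall* elaborates that inference, and its natural sense is the declared window taken as a whole. It matches section 4.1.2 and both synopsis statements.
- *Overall beside each timepoint.* This fits two visits equally well: Weeks 8 and 12 combined, then each separately.
- *Comparison with the preceding visit.* This can be formed from Week 12 against Week 8. It is a supplementary display, shown only if the interaction is significant.
- *Collection at every visit.* The visits that enter the model and the visits that enter the contrast are separate choices. An MMRM fitted to all post-baseline visits can still test the Weeks 8 and 12 contrast.
- *The phrase in section 5.2.* Twelve weeks is the treatment duration, and the phrase may mean no more than that.

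No sentence says that the primary test averages Weeks 1 and 4 or includes Follow-up.

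**The case for a change.** The strongest case for a change is that the visit list may wait for the SAP, but the protocol itself states the primary null hypothesis, and the sentence leading into it uses an undefined time frame. Two analysts could build different contrasts from it. The pooled test also gates the dose comparisons, and section 5.14 allows an unblinded efficacy interim after at least 75 completers, possibly with sponsor staff unblinded. If Follow-up were averaged in with no residual effect, even a constant on-treatment effect would shrink to 0.376 × 4/5 = 0.301 (26% reduction), with power 0.845 at r = 0.7. Fixing the phrase would cost a few words.

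Part of this stands. *Overall* is loose, the all-visit reading is possible, and under slow onset the difference would not be trivial. But it shows only that the word can be misread. It does not show that the protocol prescribes a test different from its endpoint. Choosing the all-visit contrast would mean setting aside the window declared two sentences earlier. The interim adds little: section 5.14 places its details in the SAP, the same document in which the contrast is to be written out.

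**Conclusion.** No change to the plan follows. This is an undefined word whose natural reading agrees with the declared endpoint, so it is a gap that analysts fill sensibly rather than a contradiction. A sponsor following its own stated primary inference tests pooled IW-1973 against placebo over Weeks 8 and 12. The contrast weights, the model visits and the handling of Follow-up are ordinary SAP content.

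On the natural reading nothing is lost: power for the Weeks 8 and 12 contrast is 91% to 96% for r from 0.85 down to 0.5, or 89.5% if the planning SD already describes the two-visit average. The alternative figures, from 98% down to 61% without Follow-up, depend on assumed correlations and onset profiles that the protocol neither gives nor rules out. With immediate onset and Follow-up excluded, the all-visit average would have slightly more power.

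The conclusion rests on the protocol text alone. It would need another look only if the SAP defined the primary contrast as an average over visits outside Weeks 8 and 12.

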PK Population: The PK Population will consist of all randomized patients who receive at least 1 dose of study drug and have at least 1 postdose PK parameter assessment.

Per-Protocol (PP) Population: The PP Population will consist of all ITT patients who did not have any major protocol deviations or dose reduction.

Efficacy Analyses

Corresponding with the primary efficacy objective of the trial, the primary inference for hypothesis testing is the treatment difference between the placebo group and the IW-1973 groups on the change from baseline in log UACR over Weeks 8 and 12. The primary efficacy analysis will be conducted using the ITT population using a mixed-effects model repeated measures (MMRM) analysis with change from baseline in log-transformed UACR as the response variable, treatment, site, visit, treatment-by-visit interaction, and baseline eGFR stratum as fixed effects, and baseline log UACR and baseline mean arterial pressure as covariates with unstructured as the variance-covariance structure. Treatment differences between the pooled IW-1973 dose groups and the placebo group will be estimated overall. The null hypothesis of the test will be interpreted as equality between the placebo and pooled treatment groups, and rejection of the null hypothesis as evidence that the pooled IW-1973 groups have a greater effect on lowering UACR than the placebo group. If the null hypothesis is rejected, the nature of these differences will be explored further by estimating the treatment differences between each IW-1973 dose group and the placebo group overall and at each assessment timepoint. Least square (LS) means, and LS mean differences between each

IW-1973 group and placebo, and their associated one-sided 95% confidence intervals will be calculated overall and for each assessment timepoint. The contrasts between each IW-1973 dose group and the placebo group at each assessment timepoint will be compared using a one-sided significance level of 0.05. If the treatment-by-visit interaction is significant at the 0.1 significance level, LS mean treatment differences relative to the previous visit will also be presented.

All change-from-baseline efficacy parameters will use the same MMRM model. Treatment group differences in the proportion of patients who achieved a 30% or 40% reduction in UACR from Baseline to Week 12 will be analyzed using Cochran-Mantel-Haenszel (CMH) test stratified by Baseline eGFR stratum.

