3.2 DISCUSSION OF STUDY DESIGN AND CONTROL GROUP

A double-blind, placebo-controlled, randomized study design was chosen to provide comparable treatment groups and minimal chance of selection or investigator bias in accordance with the concepts in ICH E10, Choice of Control Groups and Related Issues in Clinical Trials (International Conference on Harmonisation of Technical Requirements for Registration of Pharmaceuticals for Human Use, 2001). Placebo was chosen as the control so that the rate of spontaneously occurring AEs can be determined and to reduce the potential for bias in the reporting of AEs.

This study has a 12-week Treatment Period to compare the effects of IW-1973 to a placebo control. The treatment duration of 12 weeks is sufficient in length to observe changes in UACR and hemodynamic measures, and in addition to establish a difference in treatment effect between IW-1973 and placebo in these measures.[\(29\)](#)

Patients will be stratified by baseline eGFR to minimize the potential impact of baseline disease severity imbalance between treatment groups. Individual stopping criteria and Data Monitoring Committee safety reviews (Section [3.7](#)) have been established to ensure that dosing will stop should a safety signal be detected. Patients will have a Follow-up Visit 28 (± 3) days after the final dose of study drug to determine if any AEs have developed and if any AEs that were ongoing at the time of Discharge have resolved. In addition, at the Follow-up Visit as well at each study visit, female patients of reproductive potential will have a pregnancy test.

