3.8.6 Hemodynamics

Hemodynamic assessments will include seated BP and pulse, orthostatic (seated-to-standing) BP and pulse, and ABPM. Outside of the ABPM assessments, all other BP and pulse measurements will be taken by automated office blood pressure (AOBP); manual measurements are allowed in cases in which an AOBP machine malfunctions or is not available.

Blood pressure and pulse measurements at the Screening and Baseline Visits will be performed with patients in the seated position. Seated BPs for study eligibility will be the average of 3 measurements obtained at 2-minute intervals after the patient has been sitting quietly for at least 5 minutes.

Blood pressure and pulse measurements at the Randomization, Week 4, Week 8, End of Treatment, and Follow-up Visits will be seated-to-standing for calculation of orthostatic BP and pulse. Patients should sit quietly for at least 5 minutes before seated measurements are taken, and then assume a standing position for 30 to 60 seconds before standing measurements are taken. At the End of Treatment visit, seated predose BP will be the average of 3 measurements.

When applicable, BP and pulse measurements should be taken before blood draws. All predose BP and pulse measurements should be taken before all oral and any antihypertensive concomitant medications.

Patients will begin 24-hour ABPM at the study site during the Baseline and End of Treatment Visits and will begin 12-hour ABPM at the study site during the Week 4 and Week 8 Visits. Patients will return the ABPM equipment to the study site at the following study visit.

Baseline Visit ABPM assessment: At least 65% compliance is preferred, with no more than 10 missed readings during the day (7 am – 10 pm) and/or 3 missed readings at night (10:30 pm – 6:30 am), and no more than 6 missed readings in succession. (If a patient's ABPM assessment does not meet these criteria, the medical monitor must be contacted PRIOR to randomizing the patient.)

At the Week 4, Week 8, and End of Treatment Visits, ABPM should begin before study drug administration.

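### Does using one MMRM for every change-from-baseline efficacy parameter leave out each parameter's own baseline?

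*Protocol*

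**What the plan says.** The primary efficacy endpoint (section 4.1.2) is "Change from baseline in UACR over Weeks 8 and 12". Section 5.9 specifies its model in full:

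- **Response:** "change from baseline in log-transformed UACR as the response variable".
- **Factors:** "treatment, site, visit, treatment-by-visit interaction, and baseline eGFR stratum as fixed effects".
- **Covariates and covariance:** "baseline log UACR and baseline MAP as covariates with unstructured as the variance-covariance structure".

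The synopsis gives the same model ("baseline log UACR and baseline mean arterial pressure as covariates with unstructured as the variance-covariance structure"). Both places then extend it in one sentence: "All change-from-baseline efficacy parameters will use the same MMRM model". Neither says whether baseline log UACR stays, is replaced, or is joined by another baseline when a different parameter is analysed.

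Section 5.1 leaves additional statistical detail to an SAP that is to be finalized before unblinding. The exploratory endpoints in section 4.2 are blacked out in the public copy.

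**The concern.** A change score analysed without its own baseline is noisier than it need be, because patients who start high tend to fall and those who start low tend to rise. The primary model deals with this by including baseline log UACR. Carried unaltered to another parameter, that covariate would usually explain little, and the parameter's own baseline would be missing.

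The sentence is plural and covers all such parameters, so it is evidently meant to reach beyond UACR. Section 3.2 defends the 12-week duration as long enough to observe "changes in UACR and hemodynamic measures, and in addition to establish a difference in treatment effect between IW-1973 and placebo in these measures", and section 3.8.6 states: "Hemodynamic assessments will include seated BP and pulse, orthostatic (seated-to-standing) BP and pulse, and ABPM". Baseline MAP partly stands in for baseline blood pressure and the eGFR stratum for baseline eGFR, but no named term stands in for baseline pulse.

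On that reading, intervals for some non-UACR measures would be wider than necessary in a trial of about 50 patients per arm. Each estimate would also move with any chance imbalance in that measure at baseline.

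**Working it through.** **The plan's own figure.** Section 5.2 gives SD 0.67, difference 0.376, one-sided 0.05, 40 per arm and 20% dropout.

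- Standard error: 0.67 × √(2/40) = 0.150.
- 0.376/0.150 = 2.51, and 2.51 − 1.645 = 0.865, so power is 80.6% by the normal approximation (80.0% by the t distribution).
- 1 − exp(−0.376) = 31.3%, matching the stated 31%.
- 40/0.80 = 50 per arm, 150 in total.

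The design figure reproduces. It concerns log UACR, whose own baseline is in the model, so the point raised here does not bear on it.

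**Cost of the literal reading, one visit.** Let r be the correlation between baseline and follow-up (an assumption), with equal variance s² at both times and the named covariates unrelated to the parameter.

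- Variance of the change without own baseline: 2s²(1 − r).
- Variance with own baseline: s²(1 − r²).
- Ratio: 2(1 − r)/(1 − r²) = 2/(1 + r).

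**Cost for the average of two visits.** Section 5.9 also estimates differences overall. Assume the same r between all pairs of time points.

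- Without own baseline: s²[(1 + r)/2 + 1 − 2r] = 1.5s²(1 − r).
- With own baseline: s²[(1 + r)/2 − r²] = s²(1 − r)(1 + 2r)/2.
- Ratio: 3/(1 + 2r).

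| r | one visit: variance ratio | interval wider by | two-visit mean: variance ratio | interval wider by |
|---|---|---|---|---|
| 0.5 | 1.33 | 15% | 1.50 | 22% |
| 0.7 | 1.18 | 8% | 1.25 | 12% |
| 0.8 | 1.11 | 5% | 1.15 | 7% |
| 0.9 | 1.05 | 3% | 1.07 | 4% |

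A one-visit contrast that has 80% one-sided power with its own baseline would have Φ[(1.645 + 0.842)/√ratio − 1.645] without it: 69%, 74%, 76% and 78% down the four rows.

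**These are not upper bounds.** With a follow-up SD 0.8 times the baseline SD and r = 0.7, the one-visit ratio is (0.64 + 1 − 1.12)/(0.64 × 0.51) = 0.52/0.326 = 1.59. With a follow-up SD of 1/r times the baseline SD, it is exactly 1.

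**Partial cover from terms already in the model.**

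- *eGFR.* In a simulation with baseline eGFR assumed uniform from 30 to 75, adjusting for the three strata instead of eGFR itself gives variance ratios of 1.02, 1.01 and 1.005 at r = 0.7, 0.8 and 0.9.
- *Systolic pressure.* If baseline systolic pressure and baseline MAP correlate at q, the ratio is [(1 − r)²(1 − q²) + 1 − r²]/(1 − r²). It runs from 1.03 (q = 0.9, r = 0.7) to 1.17 (q = 0.7, r = 0.5).
- *MAP.* If MAP itself were analysed, its own baseline is already a covariate.

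**Chance imbalance.** Given a baseline difference d between arms, the unadjusted change score shifts by −(1 − r)d. With 50 per arm the standard error of d is √(2/50) = 0.2 SD, so an imbalance of one standard error moves the estimate by 0.10 SD at r = 0.5 and 0.02 SD at r = 0.9. This averages to zero over randomization. It is the same loss of precision seen from another side, not an additional one.

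**Which parameters could be affected.** The visible text narrows the field:

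- Section 5.9 gives biomarker parameters summary statistics.
- Sections 5.10.2 and 5.10.3 summarize laboratory values, pulse and blood pressure descriptively as safety data.
- Section 3.2 justifies the trial's duration and assigns no measure to a model.

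**The case for a change.** The strongest case for a change is that this is not simply detail left to the SAP. The protocol itself names a model and extends it to all change-from-baseline efficacy parameters, and nothing visible brings in another baseline. An analyst who exchanges the response must still decide what to do with baseline log UACR, and one added phrase would settle that. The algebra is sound, and for the overall contrast the loss could exceed the one-visit figure. A listing under safety summaries does not prove that a measure is absent from the efficacy analyses. HbA1c or HOMA-IR, if analysed as efficacy parameters, would bear the loss in full.

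What stands is that the sentence is loosely worded and that a clarifying phrase would do no harm. What does not stand is the step from loose wording to a faulty analysis. The specification includes its response variable, so the model that is literally the same can be fitted only to UACR. Once the response is exchanged, keeping its paired baseline fixed is the less natural reading. In the stated model baseline log UACR is there as the response's own baseline, and an analyst reusing the template would exchange the two together. The protocol neither forbids this nor contradicts it.

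**Conclusion.** No change to the plan is needed. This is a wording gap that analysts fill sensibly: same structure, matching baseline. Covariates for non-primary endpoints are ordinarily settled in the SAP, which section 5.1 says will be final before unblinding.

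Even if the covariates were kept literally, the cost would be precision only: one-visit intervals about 3% to 15% wider, and two-visit averages about 4% to 22% wider, for r from 0.9 to 0.5. Those figures assume r, equal variances and covariates unrelated to the parameter. They would be much smaller for eGFR and smaller for blood pressure. No affected parameter can be identified with certainty, because the exploratory endpoint list is not visible. The treatment contrast remains unbiased on average over randomization, and nothing about the primary UACR analysis or the sample size depends on the answer.

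### The 30%/40% UACR responder test is valid but leaves out baseline log UACR, which the primary model already uses, and so gives up a little power on a non-primary endpoint

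*Protocol*

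**What the plan says.** Protocol 5.9 defines the responder comparison as the "proportion of patients who achieved a 30% or 40% reduction in UACR from baseline to Week 12", which "will be analyzed using Cochran-Mantel-Haenszel (CMH) test stratified by baseline eGFR stratum". The synopsis repeats this ("test stratified by Baseline eGFR stratum"). No other adjustment is named, and neither place gives a significance level, a sidedness or the pairs of groups to be compared.

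The primary model in 5.9 analyzes change in log UACR with treatment, site, visit, treatment-by-visit interaction and eGFR stratum, plus "baseline log UACR and baseline MAP as covariates with unstructured as the variance-covariance structure". The other change-from-baseline efficacy parameters use that model too.

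The eGFR strata are those used at randomization (3.5.2). Section 3.2 gives the reason: "Patients will be stratified by baseline eGFR to minimize the potential impact of baseline disease severity imbalance between treatment groups". Randomization is not stratified by UACR. The primary efficacy endpoint is "Change from baseline in UACR over Weeks 8 and 12" (4.1.2), so the responder rate is not primary. It has no stated power, and 5.9.1 provides for no multiplicity adjustment.

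**The concern.** A percentage-reduction responder is a cut of the change in log UACR: the patient responds if that change is at or below ln(0.7) or ln(0.6). Measurement noise in the baseline value enters the change with a negative sign, so change and baseline are expected to be negatively correlated. The entry floor of more than 200 mg/g (inclusion criterion 6b) favours regression to the mean as well. Expressing response relative to the patient's own baseline does not remove this dependence, and eGFR stratum is a different variable that cannot stand in for it.

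The primary model handles this through baseline log UACR. Only the dichotomized form of the same quantity drops it, and no reason is given. At stake are some power and some protection against chance imbalance in baseline UACR, both available from data already collected.

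**Working it through.** **Inputs from Protocol 5.2:** "Using an estimate of standard deviation of 0.67", difference -0.376 on the log scale, 40 evaluable patients per group, one-sided 0.05, 20% dropout.

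**Assumed, not in the protocol:** mean placebo change of zero; one-sided 0.05 for the responder test; 0.67 taken as the unadjusted SD of change (5.2 does not say which it is); normal log changes; three equal eGFR strata with no prognostic value; correlation ρ between baseline log UACR and change.

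**1. The plan's own figure.** n per group = 2(1.645 + 0.842)² × 0.67² / 0.376² ≈ 39.3, so 40. Power at 40 = Φ(0.376 / (0.67 × √(2/40)) − 1.645) = Φ(0.865) = 80.6% (80.0% by the noncentral t). 40 / 0.8 = 50 per group, 150 in all. The figure reproduces.

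**2. Implied responder rates.**
- 30% cut: placebo Φ(ln 0.7 / 0.67) = 29.7%; active Φ((ln 0.7 + 0.376) / 0.67) = 51.2%.
- 40% cut: 22.3% and 42.0% in the same way.

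Unadjusted two-proportion power at 40 per group is 62.4% and 59.9%. The fall from about 80% to about 60% is therefore there before any covariate is considered; it comes from dichotomizing.

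**3. A plausible ρ.** If log UACR has equal variance at both times, ρ = −0.67 / (2 × baseline SD). If log UACR is uniform over the eligible range, SD = ln(5000/200) / √12 = 3.22 / 3.46 = 0.93, so ρ = −0.67 / 1.86 = −0.36. This only shows that −0.2 to −0.4 is a reasonable range.

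**4. Simulation, 40 v 40, 10,000 trials per cell** (Monte Carlo SE about 0.5 points). Power in %:

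| Cut | ρ | CMH by eGFR | Logistic score, eGFR only | Logistic score, eGFR + log UACR | Covariate alone |
|---|---|---|---|---|---|
| 30% | 0 | 61.0 | 62.3 | 63.3 | +1.0 |
| 30% | −0.2 | 60.9 | 62.1 | 64.2 | +2.1 |
| 30% | −0.3 | 61.6 | 62.8 | 65.6 | +2.8 |
| 30% | −0.4 | 61.7 | 63.1 | 68.2 | +5.1 |
| 40% | 0 | 60.6 | 62.2 | 62.1 | −0.1 |
| 40% | −0.2 | 60.7 | 62.1 | 62.9 | +0.8 |
| 40% | −0.3 | 60.2 | 62.2 | 63.7 | +1.5 |
| 40% | −0.4 | 61.0 | 62.7 | 65.2 | +2.5 |

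The last column compares the two logistic tests. Comparing the adjusted test directly with the CMH would credit the covariate with 1 to 2 points that come from the test's variance formula.

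**5. Pooled 80 v 40 at ρ = −0.3.** Logistic score test without and with log UACR: 74.6% to 76.9% (30% cut) and 72.0% to 74.3% (40% cut), +2.3 points each. At ρ = 0 the changes are −0.3 and −0.1.

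**6. Type I error at 40 v 40** (ρ = 0, −0.3, −0.6): 4.9-5.5% for the CMH and 5.3-6.0% for the adjusted score test. Part of the raw gain is thus bought with a slightly liberal test. With type I error equalized, the covariate adds about 1-4 points at 40 v 40 and 0-4 points pooled for ρ from −0.2 to −0.4, and essentially nothing at ρ = 0.

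**7. Chance imbalance.** The standard error of the between-group difference in mean baseline log UACR is √(2/40) = 0.22 baseline SD. At ρ = −0.36 and a mean normal density of 0.37 at the 30% cut, a one-standard-error imbalance shifts the observed responder difference by 0.36 × 0.22 × 0.37 ≈ 3 points, against an expected 51.2 − 29.7 = 21.5. At ρ = −0.2 the shift is about 1.7 points.

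**The case against.** The strongest reply is that nothing is wrong with the planned test. It is stratified by the randomization factor, needs no model for the covariate, and holds its level slightly better than the adjusted test. All of that stands. A reader might infer that leaving out baseline log UACR has no benefit at all, or that the planned test is faulty; the protocol and the calculations support neither.

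A reader might also blame the missing covariate for the fall from about 80% to about 60% power. Step 2 rules that out: the covariate recovers only a small part of the loss.

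The size of the gain depends on a correlation that the protocol does not give, and with a weak one there is nothing to recover. The endpoint is not primary, and the primary model already adjusts the continuous change for baseline UACR, so chance imbalance is dealt with where the main inference is drawn. These points limit the importance of the concern but do not remove it.

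Finally, a standardized risk difference tested by a delta-method Wald statistic is mildly liberal at this size. In simulation at 40 v 40 it rejected in 5.6-6.0% of null trials for the 30% cut and 5.9-6.1% for the 40% cut. That is a reason to test by the score statistic and to keep the CMH, but not a reason to omit the adjusted analysis.

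It could be said that a supportive model is a matter for the SAP. However, 5.9 and the synopsis themselves name the test and its only stratification factor.

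**Conclusion.** The point holds as a minor, optional improvement. The responder comparison is valid but slightly less efficient than it could be, and it departs from the sponsor's own covariate choice for the same measurement. The size is about 1-4 points of power at 40 v 40 and 0-4 points pooled, with type I error equalized. This rests on SD 0.67 and difference -0.376 from section 5.2, and on the assumed zero placebo change, one-sided 0.05 and correlation of -0.2 to -0.4. The gain is about nil if the correlation is near zero. Nothing here affects the primary analysis or the sample size, and nothing justifies removing the CMH test.

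**What to change.** In 5.9 and in the efficacy paragraph of the synopsis, add for each responder cut a logistic model with treatment, baseline eGFR stratum and baseline log UACR. Test treatment by the score test, and report the standardized (marginal) risk difference with its confidence interval, so that the effect measure is not a covariate-conditional odds ratio. Keep the CMH test stratified by eGFR alongside it.

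Stratifying the CMH further by a median split of UACR is not a good substitute: at a correlation of -0.3 it changed power by only +0.7 (30% cut) and -0.1 (40% cut) points.

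The cost is a wording change in two places and a few lines of code, settled before unblinding, with no new data. The downside is a model-based estimate with slightly higher type I error at 40 per group (about 5.3-6% against about 5%); the retained CMH serves as the check on that.
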